## LIST OF ABBREVIATIONS

ADaM	analysis data model
AE	adverse event
AED	antiepileptic drug
ALP	alkaline phosphatase
ALT	alanine aminotransferase
ANOVA	analysis of variance
AR	adverse reaction
AST	aspartate aminotransferase
BMI	body mass index
BP	blood pressure
BZD	benzodiazepine
cBZR	central benzodiazepine receptor
CDMS	clinical data management system
CI	confidence interval
CNS	central nervous system
CPMP	Committee for Proprietary Medicinal Products
CRO	contract research organization
C-SSRS	Columbia-Suicide Severity Rating Scale
CYP	cytochrome P450
DBP	diastolic blood pressure
DDI	drug-drug interaction
ECG	electrocardiogram
eCRF	electronic Case Report form
ES	Enrolled Set
EOS	End of Study
EudraCT	European Union Drug Regulating Authorities Clinical Trials
FAS	Full Analysis Set
GABA A	gamma-aminobutyric acid type A
GCP	Good Clinical Practice
GMP	Good Manufacturing Practice
HBsAg	hepatitis B surface antigen
HCV-Ab	hepatitis C virus antibody
HIV	human immunodeficiency virus

---

IB	Investigator's Brochure
ICF	Informed Consent form
ICH	International Council for Harmonisation
IEC	Independent Ethics Committee
ILAE	International League Against Epilepsy
IMP	investigational medicinal product
IUD	intrauterine device
IUS	intrauterine hormone-releasing system
LEV	levetiracetam
LLOQ	lower limit of quantification
MHRA	Medicines and Healthcare products Regulatory Agency
NCA	noncompartmental analysis
OLE	open-label extension
OTC	over-the-counter
PD	pharmacodynamics(s)
PDILI	potential drug-induced liver injury
PET	positron-emission tomography
PI	Principal Investigator
PK	pharmacokinetic(s)
PK-PPS	Pharmacokinetic Per-Protocol Set
PS	Patient Safety
PSL	Padsevonil
QTcB	QT interval corrected for heart rate using Bazett's formula
QTcF	QT interval corrected for heart rate using Fridericia's formula
REC	Research Ethics Committee
SAE	serious adverse event
SAP	Statistical Analysis Plan
SBP	systolic blood pressure
SD	standard deviation
SFU	Safety Follow-up
SOP	Standard Operating Procedure
SV2	synaptic vesicle 2
TEAE	treatment-emergent adverse event
ULN	upper limit of normal

## 1 SUMMARY

Padsevonil (PSL, previously known as UCB0942) is a novel chemical entity with selective dual synaptic vesicle protein 2 (SV2) and central benzodiazepine receptor (cBZR) site affinity. It is currently being proposed initially for the treatment of focal-onset seizures in adult patients with drug-resistant epilepsy.

Many antiepileptic drugs (AEDs) are associated with drug-drug interactions (DDIs). Preclinical data indicate that PSL metabolism is mediated mainly by cytochrome P450 (CYP) 3A4 with minor involvement of CYP2C19. Consequently, PSL exposure may be altered by CYP3A4 inhibitors. It has already been demonstrated that concomitant administration of a strong CYP3A4 inducer (carbamazepine, UP0002) significantly reduces exposure to PSL.

UP0057 is a Phase 1, open-label, fixed-sequence study in healthy study participants to evaluate the effect of a coadministered moderate CYP3A4 inhibitor (erythromycin) on the pharmacokinetics (PK) and safety of PSL.

The primary objective of UP0057 is to evaluate and compare the plasma PK of PSL in the presence and absence of erythromycin in healthy study participants. The secondary objectives include the following in healthy study participants: to assess safety and tolerability of PSL in the presence and absence of erythromycin; to evaluate and compare the plasma PK of PSL metabolites in the presence and absence of erythromycin; and to assess and compare the urine PK of PSL and its metabolites in the presence and absence of erythromycin. The exploratory objectives are to estimate the inter- and intra-study participant variability in the plasma PK of PSL and its metabolites, to evaluate and compare the venous blood and MITRA microsampling PK of PSL and its metabolite in the presence and absence of erythromycin, and to archive blood samples for genotyping of drug metabolizing enzymes and biomarkers.

UP0057 is comprised of the following periods: a Screening Period; 3 Treatment Periods, and a Safety Follow-Up (SFU) Period. The Screening Period will occur within 28 days prior to the start of Treatment Period 1. Treatment Period 1 and Treatment Period 2 each consist of 5 days of PSL treatment followed by 1-week of wash-out. Treatment Period 3 consists of erythromycin only for 3 days (Treatment Period 3a), erythromycin and PSL for 8 days (Treatment Period 3b), and erythromycin only for 4 days (Treatment Period 3c). The SFU Period is performed 7 to 10 days after the last dose of investigational medicinal product (IMP) or upon discontinuation of the study.

## 2 INTRODUCTION

### 2.1 Background

The International League Against Epilepsy (ILAE) defines drug resistance as failure of adequate studies of 2 tolerated and appropriately chosen AEDs either as monotherapy or in combination to achieve sustained seizure freedom (ILAE Classification of Epileptic Seizures, 1981). In the US, there are 3 million adults with active epilepsy (Zack and Kobau, 2017). Assuming epilepsy with focal-onset seizures in 60% of patients and resistance to AEDs in 20% to 40% of patients in the US, approximately 360,000 to 720,000 adult patients with active epilepsy in the US suffer from drug-resistant epilepsy (Giussani et al, 2016; Kwan and Sander, 2004; Semah et al, 1998). It is this drug-resistant epilepsy population that represents the greatest burden of disease for individuals, physicians, and the healthcare system.

A treatment that provides a significant reduction in seizure frequency will reduce mortality (Laxer et al, 2014) and significantly improve quality of life (Choi et al, 2014; Baker et al, 1997) by increasing patients' ability to attain basic safety, freedom from the risk of falls and injuries, and reach the milestones that most people take for granted: a feeling of belonging and social integration; the ability to form intimate relationships and a family; and having a productive and rewarding profession; or other means of self-realization.

Padsevonil is a novel chemical entity currently being developed clinically for the treatment of focal-onset seizures in adult patients with drug-resistant epilepsy. The mechanism of action for PSL is unique in comparison to available AEDs because it has selective affinity both for presynaptic SV2 proteins and for postsynaptic cBZR sites on the gamma-aminobutyric acid type A (GABAA) receptor. At presynaptic sites, PSL binds with high affinity to all 3 subtypes of the human SV2 protein (ie, SV2A, SV2B, and SV2C), and at postsynaptic sites, acts as a partial agonist, binding with moderate affinity to the cBZR sites. Whereas SV2A ligands are characterized by broad-spectrum anticonvulsant activity, GABAA receptors mediate inhibitory neurotransmission, and their allosteric modulation by cBZR sites offers robust protection against seizures.

The synergistic anticonvulsive effect observed when combining levetiracetam (LEV), an AED that binds with SV2A, with benzodiazepines (BZDs) in preclinical models (Kaminski et al, 2009) was the motivation that led to the design of PSL. In nonclinical studies, PSL administered as a monotherapy has shown higher efficacy than LEV combined with a BZD (diazepam) at matching in vivo occupancies of SV2A and cBZR, respectively. This suggests that PSL's preclinical efficacy is not only due to the combination of these 2 mechanisms of action, but that a unique interaction of PSL with SV2 proteins may also play a role.

Padsevonil is cleared via metabolism involving the CYP pathway; the formation of the 2 major metabolites, [REDACTED] and [REDACTED], is mainly mediated by CYP3A4, with potential involvement of CYP2C19. Padsevonil was also found to be a weak mechanism-based inhibitor of CYP2C19. It has been observed that PSL clearance decreased following repeated oral administration, probably as a result of the auto-inhibition of CYP2C19. Consequently, CYP3A4 is assumed to be the main enzyme involved in the metabolism of PSL at steady-state.

Recent studies in patients with refractory epilepsy showed that more than 60% of patients were treated concomitantly with 2 or more AEDs (Johannessen and Landmark, 2010). Drug-drug interactions that result in alterations in the PK of AEDs can have a profound impact on tolerability, efficacy, and safety, and can potentially result in toxicity. It is therefore important to consider and estimate at an early stage the possible interactions that may occur with the concomitant use of PSL and other drugs.

This study will evaluate the impact of a moderate CYP3A4 inhibitor, erythromycin, on the PK, safety, and tolerability of PSL and its metabolites [REDACTED] in healthy study participants.

## 2.2 Clinical studies and adverse event profile

As of 01 December 2017, PSL has been administered in 7 completed human Phase 1 pharmacology studies (N01360, N01383, N01386, UP0001, UP0002, UP0010, and UP0013) and 1 completed Phase 2 proof of concept study (EP0069). There are also 2 ongoing Phase 1 clinical

pharmacology studies (UP0036 and UP0039) and 1 ongoing Phase 2 open-label extension study (EP0073). These studies have investigated the safety, PK, and pharmacodynamics (PD) of single and multiple ascending doses of PSL, and the potential interaction of PSL with food, valproic acid, carbamazepine, and other AEDs. Position-emission tomography (PET) investigations have been performed to evaluate the GABAA receptor occupancy at 2 steady state PSL dose levels and SV2A occupancy at different single PSL dose levels and times postdose in healthy study participants.

In the PSL Phase 1 program completed thus far, 129 healthy study participants and 20 study participants with epilepsy (male and female) have been exposed to PSL at single doses up to 490mg (26 healthy study participants) and repeated doses up to 400mg bid for up to 12 days (103 healthy study participants and 20 study participants). In EP0069, 55 study participants were exposed to repeated doses of PSL up to 400mg bid during the maintenance phase of the study. A total of 42 of the 55 study participants in EP0069 have enrolled in EP0073, during which they are allowed to adjust their PSL dose.

The safety findings to date suggest that the adverse events (AEs) experienced by study participants receiving single and repeated doses of PSL are limited principally to central nervous system (CNS) effects and that these are consistent with the known pharmacology of PSL, ie, similar to AEs produced by SV2A- and GABAA-targeting AEDs. The AEs tend to be dose-related in frequency and intensity, self-limiting, and tend to decrease in intensity over the first few days of dosing.

The psychiatric findings currently reported across the Phase 1 and Phase 2 studies with PSL are consistent with the AE profile of other AEDs, including other SV2A ligands. Acute psychiatric effects occurred in 3 study participants administered PSL (2 in Phase 1 and 1 in Phase 2). The events were transient, acute, and required admission to psychiatric care and antipsychotics. No definite dose relationship could be determined, and the events occurred after variable periods of time after the first administration of PSL. The occurrence of these behavioral AEs highlights the need to consider the possibility of significant psychiatric AEs and to maintain vigilance for them.

With regard to cardiovascular effects, minor, transient, reductions in blood pressure (BP) were observed in the Phase 1 and Phase 2 PSL studies; however, these were not clinically meaningful and resolved without intervention. The degrees of reduction seen in both systolic and diastolic BP are consistent with the GABAA-targeted mechanism of action of PSL and do not appear likely to have a clinically significant effect in therapeutic use (Jones et al, 1979). In regard to electrocardiogram (ECG) results, all nonclinical and clinical Phase 1 and Phase 2 cardiac data in totality were reviewed by an expert cardiologist consultant whose opinion was that “overall, there is no clear evidence that PSL is associated with any increase in incidence of ectopy, change in QT interval corrected for heart rate changes (QTc), or clinically-significant arrhythmia in clinical trials to date”. Echocardiographic screening of study participants at Baseline (to exclude study participants with valvulopathies) and ongoing echocardiographic monitoring during treatment and posttreatment has been implemented in the Phase 2 studies. No major findings were observed in the completed EP0069 study or the ongoing open-label extension study, EP0073. Cardiac monitoring (eg, ECGs, vital signs, echocardiograms) is planned throughout the duration of the PSL development program in order to better understand and mitigate any risks.

In general, the safety profile of PSL has been consistent with the pharmacological properties of the drug and with dose-escalation studies of CNS compounds in regards to the type and severity of nervous system and psychiatric AEs reported, with most AEs reported as mild or moderate.

The overall safety profile during the clinical program to date, as well as preclinical and clinical experience with PSL, can be found in the Investigator's Brochure (IB).

### 2.3 Risk assessment

Padsevonil is mainly metabolized via CYP3A4. Safety pharmacology studies have shown no major adverse effects on the respiratory and central nervous systems when administered orally in single-dose safety pharmacology studies (rats) and in repeat dose toxicity studies (rats, dogs). A slight prolongation of QTc was found in a 4-week study in dogs at 30mg/kg bid; however, it was not confirmed in a 13-week study (animals monitored by external telemetry) or a 39-week study at doses up to 50mg/kg bid, with free plasma concentration far above those reached in healthy study participants. Small, transient increases in heart rate and changes in arterial pressure (hypertension in rats and hypotension in dogs) occurring mainly from single doses are likely related to exaggerated GABAA pharmacologic activity.

In the 39-week dog toxicity study, subtle cardiac microscopic findings, consisting of minimal valvular inflammatory cell infiltration, or minimal to slight epithelial inflammation/fibroplasia of the epicardium in the right atrium, were seen in the heart of one-third of treated dogs without dose relationship. These findings were not seen in the 13-week study. Findings were subtle, focal, and not associated with any clinically significant cardiovascular changes. These findings did not cause any biological or clinical consequences in the animals in this study and were thus not considered to be adverse. This conclusion was supported after comprehensive review of the data by 5 nonclinical pathologists (including a cardiovascular expert pathologist). Additionally, external advice on the potential human implications was sought from a British Heart Foundation Professor of Cardiology. It was concluded that short-term exposure should not lead to any relevant abnormality or clinical disease, and even with long-term exposure the potential hazard and likelihood of an adverse pericardial or valvular effect in humans is extremely low.

Padsevonil is neither teratogenic nor embryotoxic in rats and rabbits. There was no effect on reproductive organs, including sperm analysis, following long-term administration (up to 26 weeks in rats and 39 weeks in dogs).

The preclinical pharmacology studies indicated that the metabolism of PSL may be affected by extrinsic influences on the CYP3A4/CYP2C19 pathway. In order to mitigate any risk caused by these interactions, medication or dietary ingredients that induce, inhibit, or are a substrate for the CYP3A4/CYP2C19 pathways are restricted. Further details are provided in [Section 7.8.2](#) and [Section 7.8.3](#), respectively.

In clinical trials, PSL had a good safety profile. There were no deaths. Adverse events experienced by study participants receiving single and repeated doses of PSL were limited principally to CNS effects and that these were consistent with its known pharmacology. Adverse events were dose-related in frequency and intensity, self-limiting, and tended to decrease in intensity over the first few days of dosing. Some new AEs (mainly headache and sleep disturbance) developed after dose discontinuation with PSL in the Phase 1 studies, indicating a potential withdrawal syndrome. These have been mild, transient, not dose-related and not of clinical concern.

The occurrence of acute psychiatric serious adverse events (SAEs) (delirious syndrome, mania-like symptoms, and acute psychosis) in 3 study participants administered PSL highlights the need to maintain vigilance for such events. Reported acute psychiatric effects are consistent with adverse effects of other anticonvulsant drugs with various mechanisms of action. These SAEs were transient, acute, and required clinical intervention (admission to psychiatric care and antipsychotics). In healthy study participants, those SAEs occurred early after initiation of PSL done without titration; in 1 study participant, symptoms worsened upon abrupt drug discontinuation. Only in 1 out of 68 epileptic study participants exposed to PSL, a psychotic effect emerged a few weeks following dosing start after improvement in seizure control. This suggests a “forced normalization” phenomenon, which is described with other AEDs in resistant patients and is not unexpected with a potent AED (Loganathan et al, 2015; Clemens, 2005). The mitigation plan for acute psychiatric effects involves gradual titration and taper, known to improve tolerability of AEDs.

Despite the occurrence of ECG findings such as ectopies (asymptomatic, not requiring clinical intervention), there are no current data suggesting that PSL has an adverse effect on cardiovascular function other than a minimal lowering effect on BP. The degrees of reduction of both supine blood pressure (SBP) and diastolic blood pressure (DBP) are consistent with the GABAA-targeted mechanism of action of PSL and do not appear likely to have a clinically significant effect in therapeutic use. As a precaution from preclinical and clinical findings of non-clinically significant ECG abnormalities and hypotension, ECGs and vitals are being assessed frequently in current clinical studies.

There is no benefit for healthy study participants to participate in this study. However, the information obtained from this study will inform decisions on safe and effective doses of PSL to be given to epileptic study participants in future studies. The Sponsor will immediately notify the Principal Investigator (PI) and regulatory agencies if any additional safety or toxicology information becomes available during the study.

## **2.4 Urgent safety measures**

In accordance with UK Law (Medicines for Human Use [Clinical Trials] as amended: SI 1031 Part 4 Section 30), the Sponsor and Investigator may take appropriate urgent safety measures in order to protect the study participants of a clinical study against any immediate hazard to their health or safety. If such measures are taken, the Sponsor shall immediately (no later than 3 days from the date the measures are taken) give written notice of the measures taken and the circumstances giving rise to those measures to the licensing authority and the relevant ethics committee.

### 3 STUDY OBJECTIVES

#### 3.1 Primary objective

The primary objective of this study is to evaluate and compare the PK of PSL in the presence and absence of erythromycin in healthy study participants.

#### 3.2 Secondary objectives

The secondary objectives of this study are to:

- Assess the safety and tolerability of PSL in the presence and absence of erythromycin in healthy study participants
- Evaluate and compare the plasma PK of PSL metabolites, [REDACTED] in the presence and absence of erythromycin in healthy study participants
- Assess and compare the urine PK of PSL and its metabolites [REDACTED] and [REDACTED] in the presence and absence of erythromycin in healthy study participants

#### 3.3 Exploratory objectives

The exploratory objectives of this study are to:

- Estimate the inter- and intra-study participant variability in the plasma PK of PSL and its metabolites following administration of PSL in the presence and absence of erythromycin
- Evaluate and compare the venous blood and MITRA microsampling (dried blood) PK of PSL and its metabolite [REDACTED] following administration of PSL in the presence and absence of erythromycin
- Archive blood samples for genotyping of drug metabolizing enzymes and biomarkers

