#### **5.2.2.1 Treatment Period 1 and Treatment Period 2 (Day 1 to Day 11 and Day 12 to Day 22)**

Treatment Period 1 and Treatment Period 2 each consist of 5 days of treatment, followed by 1 week of wash-out.

During Treatment Period 1 and Treatment Period 2, study participants will receive PSL 100mg bid for 4 days (Day 1 to Day 4 and Day 12 to Day 15). On the fifth day (Day 5 and Day 16), 100mg of PSL will be given as a single dose in the morning. Study participants then enter 1 week of wash-out (from the evening of Day 5 to Day 11 and evening of Day 16 to Day 22).

Predose and postdose blood (venous and MITRA) and urine samples will be collected for PK analysis throughout the study (more details are provided in [Section 5.3](#)).

On Day 7 and Day 18, during the wash-out period, study participants will be discharged at the Investigator's discretion. Study participants may continue being confined to the unit at the Investigator's discretion. Study participants will check back into the unit on Day 10 and Day 21. Study participants will undergo the triplicate 12-lead ECG run-in on Day 11 and Day 22.

Study participants will be asked about the occurrence of AEs at check-in on Day 10, and via telephone contact on Day 20.

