#### **5.2.2.2.2 Treatment Period 3b (Day 26 to Day 33)**

Study participants will remain confined to the unit throughout Treatment Period 3b. Coadministration of PSL (100mg bid) and erythromycin (500mg bid) will begin on Day 26. Combination therapy will last for 8 days (Day 26 to Day 33). On Day 33, study participants will only receive a single dose of PSL 100mg in the morning, in addition to erythromycin 500mg bid. Predose and postdose blood (venous and MITRA) and urine samples will be collected for PK analysis throughout the coadministration period (ie, Treatment Period 3b; see [Section 5.3](#) for more details).

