### **5.3.1 Venous blood**

Venous blood samples for PK analysis will be performed as follows:

- Predose and 0.25h, 0.5h, 0.75h, 1h, 1.25h, 1.5h, 2h, 3h, 4h, 6h, 8h, and 12h post first dose of PSL during each Treatment Period (Day 1, Day 12, and Day 26)
- Predose and 0.25h, 0.5h, 0.75h, 1h, 1.25h, 1.5h, 2h, 3h, 4h, 6h, 8h, 12h, 24h, 36h, 48h, and 72h post last dose of PSL during Treatment Period 1 (Day 5) and Treatment Period 2 (Day 16)

- Predose and 0.25h, 0.5h, 0.75h, 1h, 1.25h, 1.5h, 2h, 3h, 4h, 6h, 8h, 12h, 24h, 36h, 48h, 60h, 72h, 96h, and 120h post last dose of PSL during Treatment Period 3b (on the morning of Day 33)

Additional PK trough samples will be taken immediately prior to each morning dose of PSL during Treatment Period 1 (Day 2 through Day 4) and Treatment Period 2 (Day 13 through Day 15) and each morning combination dose during Treatment Period 3b (Day 27 through Day 33).

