The primary comparison of interest is the similarity of plasma PK parameters (C_{max} , $AUC_{(0-12)}$, $C_{max,ss}$, and AUC_{τ}) for PSL between treatment periods with erythromycin (Treatment Period 3b) and PSL without erythromycin (treatment periods 1 and 2). This will be assessed using a linear mixed effects model with treatment periods (1, 2 and 3b, comparing with vs without erythromycin periods) fitted as fixed effects and subject fitted as a random effect. The mixed effects model will be using Kenward-Rodgers degrees of freedom. Point estimates for the ratio of geometric means with and without erythromycin (Period 3b compared to periods 1 and 2) and the respective 2 sided 90% CIs will be computed using the least squares means and the root mean squares of error from the mixed effects model, based on of the log-transformed data with subsequent exponential transformation. In addition point estimates for the ratio of geometric means and the respective 2 sided 90% CIs will be presented for the following comparisons:

- Treatment Period 1 (PSL) compared to Treatment Period 3b (PSL + erythromycin)
- Treatment Period 2 (PSL) compared to Treatment Period 3b (PSL + erythromycin)

Treatment Period 1 (PSL) compared to Treatment Period 2 (PSL) Ping pong plots will be displayed for each of the PK parameters (C_{max} , $AUC_{(0-12)}$, $C_{max,ss}$, and AUC_{τ}) against treatment of PSL with (Treatment Period 3b) and without erythromycin (treatment periods 1 and 2, separately).

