9.3 Analysis of other pharmacokinetic variables

The other PK variables and their analysis are the followings:

- Inter- and intra-study participant coefficients of variation (variability) in PK parameters C_{max} , $AUC_{(0-12)}$, $C_{max,ss}$, and AUC_{τ} for PSL and its metabolites

Inter-study subject and intra-study subject variability on the PK parameters for PSL and its metabolites will be estimated from the mixed effects analysis described in [Section 9.1](#). The point estimate (CV%) and 2-sided 90% CI for the inter-subject variability will be derived from the subject effect of the variance covariance matrix, and for the intra-subject variability, the point estimate (CV%) and 2-sided 90% CI will be derived from the residual effect of the variance-covariance matrix.

- Pharmacokinetic parameters C_{max} , $AUC_{(0-12)}$, $C_{max,ss}$, and AUC_{τ} (and profile) data derived from MITRA dried blood concentration for PSL and its metabolite (only [REDACTED])
- The blood concentrations and blood PK variables for PSL and its metabolite based on the MITRA microsampling will be summarised and plotted as described in [Section 9.1](#).
- As exploratory analysis, point estimates for the ratio of geometric means for the PK parameters C_{max} , $AUC_{(0-12)}$, $C_{max,ss}$, and AUC_{τ} for PSL based on the MITRA dried blood microsampling compared to the plasma conventional venous sampling along with the 2 sided 90% CIs will be computed using the least squares means and the root mean squares of error from a specific linear mixed effects model, based on of the log-transformed data with subsequent exponential transformation for the following periods:
 - Overall: conventional venous compared to MITRA
 - Period 1: conventional venous compared to MITRA
 - Period 2: conventional venous compared to MITRA
 - Period 3b: conventional venous compared to MITRA
- Scatter plots of the MITRA dried blood concentrations versus venous plasma concentrations for PSL and its metabolite will be presented. Furthermore a linear regression plot of the MITRA dried blood concentrations and venous plasma concentrations for PSL and its metabolite including the regression lines for the mean along with 90% confidence intervals will be presented for the log data.

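### With one combination value per participant, intra-participant variability with erythromycin cannot be estimated for the four modelled PK parameters, and the residual CV reported as intra-subject also carries any variation in the interaction

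*Protocol*

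**What the plan says.** Protocol 3.3, repeated in SAP 2.1.3, sets an exploratory aim that covers between-participant variability together with "intra-study participant variability in the plasma PK of PSL and its metabolites following administration of PSL in the presence and absence of erythromycin".

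The design supplies the following data:
- **PSL alone:** Periods 1 and 2, with full profiles on Days 1 and 5 and on Days 12 and 16 (Protocol 5.2.2.1 and 5.3.1).
- **PSL with erythromycin:** Period 3b only, with full profiles on Days 26 and 33 (Protocol 5.2.2.2.2 and 5.3.1).

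In each period the first-day profile gives Cmax and AUC(0-12), and the last-day profile gives Cmax,ss and AUCtau.

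SAP 9.1 analyses each log-transformed parameter in one mixed model, with periods 1, 2 and 3b "fitted as fixed effects and subject fitted as a random effect". It has no participant-by-treatment term and no treatment-specific residual. SAP 9.3 takes the inter-subject CV from the subject effect, while the intra-subject figure and its two-sided 90% interval "will be derived from the residual effect of the variance-covariance matrix". Protocol 12.3.1 likewise takes both kinds of variability from the three-period analysis. No variance estimate from Periods 1 and 2 alone is planned, and SAP 3.9 (changes to protocol-defined analyses) does not mention this objective.

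**The concern.** An intra-participant variance needs at least two comparable values per participant under the same condition. The two Period 3b profiles do not provide this, because they feed different parameters. The objective therefore promises a quantity that the design cannot supply for the four modelled parameters.

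The number reported in its place has a second problem. With no participant-by-treatment term, any person-to-person difference in the size of the interaction goes into the residual. A reader who takes that CV as the consistency of PSL exposure within a person, or uses it to plan a later study of PSL alone, could work from the wrong figure. Differences between people are plausible: Protocol 2.1 describes CYP3A4 metabolism with potential CYP2C19 involvement and probable auto-inhibition of CYP2C19. The documents do not quantify them.

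**Working it through.** **Notation (log scale).** s²_R is the within-participant variance with PSL alone, s²_T the within-participant variance with erythromycin, s²_D the between-participant variance of the true log interaction ratio, and s²_B the between-participant variance. CV = √(exp(variance) − 1).

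**1. What the plan's own variability figures supply.** Protocol 12.7 and SAP 2.4 give CV 140%, correlation 0.5, half-width 0.75, conditional probability 80% and α = 0.05, for n = 20. Taking SD = 1.40, SD_diff = 1.40 × √(2(1 − 0.5)) = 1.40. The conditional probability that t × S/√n ≤ 0.75 is 0.770 at n = 19 and 0.829 at n = 20, so n = 20 is reproduced. These inputs describe the total spread of a with/without pair. They do not divide it into s²_R, s²_T and s²_D, so no figure for s²_D can be taken from the plan.

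**2. Identifiability.** If the individual interaction is independent of baseline level, Var(Period 3b) = s²_B + s²_D + s²_T, and the covariance with Periods 1 and 2 is s²_B. Only the sum s²_D + s²_T is visible. Take s²_B = 1.00 and s²_R = ln(1 + 0.30²) = 0.0862, and compare two cases:
- s²_T = 0.0862 + 0.15 and s²_D = 0
- s²_T = 0.0862 and s²_D = 0.15

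Both give Var(Period 3b) = 1.24, covariances of 1.00 and an expected residual of 0.0862 + 0.15/3 = 0.136. The data cannot tell them apart, so adding a participant-by-treatment term or treatment-specific residuals would not recover s²_T.

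**3. What the residual estimates (complete data).** The residual averages two normalised within-participant contrasts:
- (P1 − P2)/√2 has variance s²_R.
- √(2/3) × (P3b − (P1 + P2)/2) has variance (2/3)(s²_T + s²_D) + (1/3)s²_R.

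Their average is (2/3)s²_R + (1/3)(s²_T + s²_D). If s²_R = s²_T = s²_W, this is s²_W + s²_D/3. Simulation with 20 participants and 20,000 trials agreed (0.1358 against 0.1357, and 0.1601 against 0.1606, in two scenarios).

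**4. Size, over assumed values.** For a true CV of 30% and an SD of 0.5: 0.0862 + 0.25/3 = 0.1695, so CV = √(exp(0.1695) − 1) = 43%. The other cells use the same formula, with s²_W = ln(1.04) = 0.0392 for 20% and ln(1.16) = 0.1484 for 40%.

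| Assumed true intra-CV | SD 0 | SD 0.2 | SD 0.3 | SD 0.5 |
|---|---|---|---|---|
| 20% | 20% | 23% | 27% | 36% |
| 30% | 30% | 32% | 35% | 43% |
| 40% | 40% | 42% | 44% | 51% |

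(SD is that of the individual log interaction ratios.)

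**5. The residual can also fall below the PSL-alone CV.** With s²_R = 0.0862 (30%), s²_T = 0.0392 (20%) and s²_D = 0: (2/3)(0.0862) + (1/3)(0.0392) = 0.0705, a CV of 27%.

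**6. Periods 1 and 2 alone.** In simulation their contrast returned 30.0% in every scenario with a true PSL-alone CV of 30%. It has n − 1 = 19 degrees of freedom at 20 completers. The 90% limits are 19 × 0.0862 divided by the upper and lower 5% points of chi-square on 19 df, which gives CVs of about 23.6% to 41.9%.

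**The case against.** **Already reported by period.** A reader might infer that no variability measure is split by erythromycin. That is not so. SAP 9.1 gives geometric CVs by treatment period, SAP 3.6 keeps Periods 1, 2 and 3b separate for PK, and SAP 9.2 extends this to metabolites. Total spread with erythromycin is therefore planned; only the model-based components are pooled.

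**Troughs.** Ctrough is sampled each morning on Days 27 to 33 under the combination (Protocol 5.3.1) and summarised by day (SAP 9.3). To say that nothing about within-participant variability with erythromycin can be learned would go too far. Still, no variance component is planned from the troughs, and they do not cover the four parameters to which SAP 9.3 applies the CVs.

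**A pooled reading.** Protocol 4.1.3 lists the variability variable without a with/without split, so the objective could mean one overall estimate. That is a fair reading of loose wording. It gives an intra-participant CV only if within-participant variances are equal and the interaction is uniform, and the SAP states neither condition.

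**The residual has its own use.** This objection stands. A later two-period interaction study has effective error variance s²_W + s²_D/2. With a true CV of 30% and SD 0.5, that is 0.0862 + 0.125 = 0.2112, a CV of 48%. The three-period residual gives 43% and Periods 1 and 2 alone give 30%. Replacing the residual would understate the error for such a study.

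**Carryover.** Protocol 2.1 describes probable CYP2C19 auto-inhibition, and one week of wash-out separates Periods 1 and 2. A fixed period effect removes average carryover but not individual differences in it. The documents give no recovery data, so Periods 1 and 2 cannot be called a proven clean replicate.

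**Conclusion.** The point holds for Cmax, AUC(0-12), Cmax,ss and AUCtau, as a minor one. Non-identifiability with erythromycin follows from the design and needs no numerical assumption. The content of the residual follows from the SAP model. Its excess over the true intra-CV is conditional: 2 to 13 percentage points for an assumed true 30% and log-ratio SDs of 0.2 to 0.5, with equal within-participant variances. It is zero if the interaction is the same in everyone.

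Three stronger readings are not supported:
- **That the residual CV is always inflated.** It can lie below the PSL-alone CV if within-participant variance is lower with erythromycin.
- **That the planning figures imply a residual CV near 69%.** On the log scale, ln(1 + 1.4²) × 2 × (1 − 0.5) = 1.085 = 2s²_W + s²_D. Assuming a true CV of 30% then gives s²_D = 0.913 and a residual of 0.0862 + 0.304 = 0.390. But that 30% appears nowhere in the documents. The same inputs with s²_D = 0 give an intra-CV of 85% and no inflation. The log-scale reading also yields n = 13, not the stated 20.
- **That the interaction ratio or its confidence interval is wrong.** This point concerns only the variability estimate and its label.

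**What to change.** 1. In Protocol 3.3 and SAP 2.1.3, limit the intra-participant objective for the four parameters to the absence of erythromycin.
2. In SAP 9.3, add an intra-participant CV with 90% CI, and the matching inter-participant CV, from a model of Periods 1 and 2 only. Label both as PSL alone and state the assumption of no participant-specific carryover.
3. Keep the three-period residual CV, but label it as within-participant plus participant-by-erythromycin variability. Note that it is the more relevant input for a later interaction study.
4. Label the already planned Period 3b geometric CV as total variability, within-participant variability included.
5. Record the change in SAP 3.9, because Protocol 12.3.1 takes variability from the three-period analysis.

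The cost is wording in both documents and one extra simple model per parameter and analyte, with no new samples, visits or participants. The PSL-alone CV rests on n − 1 rather than 2(n − 1) degrees of freedom (19 rather than 38 at 20 completers), so its interval is wider.
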